6.2 Study Enrollment Procedures

This study will be conducted on a study platform that is already in place at the Mayo Clinic Rochester. Patients identified with a diagnosis of acute myocardial infarction and subsequent coronary angiography will be enrolled. Any potential study candidates will be identified based on the eligibility criteria listed above. A screening log will be kept and secured electronically. Those potentially eligible will be recorded by clinic number and exclusion criteria will be checked. If any are met, the specific reason will be marked, otherwise a commentary will be entered for those who are eligible but do not wish to participate. Those patients who agree to participate will be asked to provide written consent. The study details will be outlined. It will be made clear that at this point there are no data whether the intervention approach leads to superior clinical outcomes and this very fact provides the rationale for this trial.

7. STUDY INTERVENTIONS

Interventions, Administration, and Duration

Patients will be randomized to either standard medical therapy or standard medical therapy + Smartheart home telemonitoring device. The device will be supplied by the "SHL" telemedicine for each patient in the intervention group for the period of 90 (+/-7) days from the randomization. Patients will be followed for 90 (+/-7) days. At randomization and at the end of the study period the patients will be asked to fill out quality of life questionnaire and return back the Smartheart device by mailing back the device in the padded box covered by

[figure not shown]

Figure 2. Call work-flow

insurance in case it is damaged upon receipt to Mayo Clinic. Medications during the study period will be prescribed by the treating physician, no change of medications will be performed by the study team.

The SmartHeart, developed by SHL Telemedicine Ltd., was approved by the FDA on 2012 (K113514). It is a personal, hand-held device, enabling an individual to immediately transmit a 12-lead ECG from anywhere and anytime, using a smart phone application, to a physician's office, hospital or monitoring center. The ECG output from Smartheart device was compared to standard 12 lead ECG recordings and was found to be reliable. Data will be labeled with a subject's medical record number and by date of transmission. The data will be uploaded from Smartheart device to the US cloud (located in USA), and sent by email directly to designated Mayo Clinic CICU NP/PA smartphone devices email address. The smartphone device will be carried by the NP/PA 24/7 and will give a loud alert for every incoming ECG. The ECG data will be uploaded and accessible in the patient's EPIC EMR.

The smart phone application will send push notifications to the patients to remind them to perform test ECG at Week 1, Week 2, and Week 4 (optional, if patient has not performed Week 2 ECG). Patients will also be notified every other day after Week 1, if not completed.

8. STUDY PROCEDURES

8.1.1 Screening Evaluation

Acute myocardial infarctions patients identified on cardiology service will be evaluated for enrollment. These patients will be approached by a trained research member who will present the background, rationale, and details of the study. A single informed consent form will be used that describes both the screening and study procedures. Those who consent will be asked additional questions of their past medical history and their records will be reviewed to identify any exclusion criteria. If any are present, these will be charted in the screening log. For those who are eligible but refuse, a comment will be added to the screening log detailing the reason for non-participation.

8.1.2 Enrollment, Baseline, and/or Randomization

All patients who consent to the study are considered to be enrolled as of the date of the consent.

Baseline Assessments- comprises a review for any cardiovascular diseases or risk factors, home medications. Additional data will be collected: type of AMI (location: anterior, inferior, posterior, lateral), troponin levels, baseline ECG, left ventricular function by echocardiography, Canadian Classification scale (CCS) of Angina(class I, II, III IV) .

Randomization- will be done once all inclusion and exclusion criteria are reviewed and the patient meets eligibility criteria. Patient and treating cardiologist will be informed which study group the patient was assigned. Patients assigned to group 1 will be discharged with standard medical therapy as indicated by AHA/ACC guidelines in post AMI patients treated with or without PCI. Patients in group 2 will be discharged with the standard medical treatment as indicated by AHA/ACC guidelines in post AMI patients treated with or without PCI plus they will receive the Smartheart 12 lead ECG home telemonitoring device for the period of 90 days (+/-7). Those patients will have short explanation on how the device works, how to adjust it on the chest and how to transmit the ECG.

A post-study questionnaire will be administered to patients randomized to the device group to collect feedback on their experiences with the device. Participation is voluntary, and responses will be anonymized to ensure confidentiality. The inclusion of this questionnaire will not impact the primary study objectives or patient safety.

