Number of Subjects	240 patients in total, enrolled over one-two years

Inclusion and Exclusion Criteria	
Inclusion criteria:
 
 • ≥18 years of age, • Acute myocardial infarction, both STEMI and non-STEMI • Able to use the home ECG telemonitoring • Must have smartphone device with home wi-fi/mobile internet which allows 24/7 ability to transmit ECG • Caring family member who will be able to help/perform the ECG in case the patient himself won't be able to do it • Planned to be discharged home by the treating team 
Exclusion criteria:
 
 • No ability to use the device at home • No smartphone device or home wi-fi/mobile internet which prevent 24/7 ability to transmit ECG • Cannot download the smartheart app • No support in home environment • Out of hospital cardiac arrest: secondary to a non-shockable rhythm, unrelated to an acute coronary syndrome, or with any level of neurologic damage. • Resident of nursing home or acute care facility • Uninterpretable ECG at discharge – left bundle branch block (LBBB), pacemaker or implantable cardioverter defibrillator (ICD) with pacing dependence. • Patients who are planned for staged PCI after the index hospitalization
Study Product, Dose, Route, Regimen	Prior to discharge patients will be 1:1 randomized to standard medical therapy or standard medical therapy + 12 lead ECG Smartheart telemonitoring device.
Duration of Administration	Patients will receive the device for the period of 90 (+/-7) days .
Reference therapy	Group 1 will serve as the reference group
Statistical Methodology	Inter-group differences in the rates of the primary combined endpoint will be analyzed by the Chi square test.

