5. STUDY DESIGN

This study will be conducted as a prospective, randomized pilot study in patients with acute myocardial infarction which have undergone coronary angiography with two study groups (Figure 1):

- **Group 1 (control group):** standard clinical practice medical therapy at discharge, including double antiplatelet therapy (DAPT), high potency statins and if indicated, beta blockers.
- **Group 2 (intervention group):** standard clinical practice medical therapy as above plus the Smarheart home-telemonitoring 12 lead ECG device.

Figure 1: Trial outline

Patients will be randomized at discharge to standard medical therapy (DAPT, high potency statins and beta blockers) or the standard medical therapy plus the Smartheart home-telemonitoring 12 lead ECG device. The intervention group will have instructions and explanation, prior discharge, how to use the device and will be guided to have two device testing's at home during the first two weeks after discharge. In case of any symptoms, including but not limited to chest pain, shortness of breath, sensation of irregular heart beats and near fainting during the 90 days post discharge the patient will record a 12 lead ECG at home and transmit it directly to Saint Mary's Hospital CICU designated study NP/PA, which is available 24/7, the ECG will be read by the NP/PA (with the support of the CICU consultant). Communication with the patient will be through the study designated CICU NP/PA, which will call the participant, record short history of the medical emergency and provide the patient with appropriate directions according to the ECG finding, medical urgency and study protocol. The CICU NP/PA will call the patient as soon as possible after receiving the ECG to the study email inbox.

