8.1 Schedule of Evaluations

Assessment	Screening, Enrollment, Randomization: pre-discharge (Day 0)	Week 1 (-3,+6 days)	Week 2 (-3,+6 days)	Week 4 (-3, +6 days)	Day 90 (Final) (+/- 7 days)
Informed Consent Form	X (R)				
Demographics	X				
Medical History	X				
Vital signs	X				
Physical Examination	X				
Current Medications	X				
Blood Chemistries	X				
Electrocardiogram	X				
Echocardiogram	X*				
Inclusion/Exclusion Criteria	X (R)				
Enrollment/ Randomization	X (R)				
Providing Device + Instructions	X (R)				
Quality of Life questionnaire (day 0)	X (R)				
Follow-up ECG and training call		X (R.S.)	X (R.S.)	X (R.S.Q)	
End of participation phone call, will include:					X (R)
• ED visits/Hospitalizations/MACE data /ccs					X (R)
• Current medications and if changed lately					X (R)
• Quality of Life questionnaire (day 90)					X (R)
Device collection (patient sending by mail)					X (R)

X Performed as standard of care (not specific for research)

X* If performed after the AMI event and pre-discharge

X (R) Research related only

X (R.S.) Research – Study group related only

X (R.S.Q) Research – Study group related only, depends on the need of further training beyond the first two tests.

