9.5.1.1. Primary outcome measures

The combined primary endpoint of the trial is the rate of ED visits, hospital readmission, and any of the downstream testing modalities (echocardiogram, stress test or coronary CT, or invasive coronary angiogram) from discharge after index hospitalization for MI to 90 days of follow-up between group 1 and group 2.

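### The treating cardiologist learns the arm before the patient leaves, and nothing requires planned follow-up tests, which may count as primary events, to be recorded first

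*Combined protocol and SAP*

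**What the plan says.** **Disclosure.** Section 8.1.2 randomizes once eligibility is confirmed and then states: "Patient and treating cardiologist will be informed which study group the patient was assigned". Discharge is described after that step.

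**Timing.** Three places differ. The Study Summary has "Prior to discharge patients will be 1:1 randomized to standard medical therapy or standard medical therapy + 12 lead ECG Smartheart telemonitoring device". The Schedule of Evaluations heads its first column "Screening, Enrollment, Randomization: pre-discharge (Day 0" (the bracket closes in the original). Section 5 begins its version "Patients will be randomized at discharge to standard medical therapy (DAPT, high potency statins and beta blockers", that is, at discharge and not before it.

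**Endpoint.** Section 9.5.1.1 combines ED visits, readmission and "any of the downstream testing modalities (echocardiogram, stress test or coronary CT, or invasive coronary angiogram) from discharge after index hospitalization". The Study Summary (Aim 1), Section 3.1 and Section 9.2 limit the testing component to tests that are related, without saying how that is judged. Section 13 provides for no adjudication committee.

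**Clinical decisions.** The Study Summary lists "Planned to be discharged home by the treating team" as an inclusion criterion; Section 6.1 omits it. Section 7 adds: "Medications during the study period will be prescribed by the treating physician, no change of medications will be performed by the study team". Planned staged PCI is an exclusion. No other planned follow-up procedure is mentioned.

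**The concern.** The proposed mechanism is that a patient with symptoms sends an ECG and is triaged by phone. A follow-up test planned at discharge is decided before any ECG is sent. If whoever plans it knows the arm, knowing that a home ECG is available could mean fewer tests planned for device patients, or more for controls. Under Section 9.5.1.1 each such test is a primary event.

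The schedule shows one concrete route. The baseline echocardiogram is collected only if it was done after the infarction and before discharge. An echocardiogram done in hospital is baseline data. The same examination deferred until after discharge is an event under Section 9.5.1.1.

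The chi-square comparison in Section 9.6 cannot tell a test avoided by triage from a test never planned because the arm was known. Both would be reported as a device effect.

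**Working it through.** **Inputs from the protocol**
- 120 per arm, control event rate 48%, relative reduction 37.5%, beta below 0.2, alpha below 0.05 (Section 9.2). Sidedness is not stated; two-sided is used here.
- 24% with an ED visit or readmission by 90 days (Section 9.2).
- Chi-square test (Section 9.6).

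**Assumptions, not in the protocol**
- A proportion q of control patients, 20% to 50%, has a listed test planned by a clinician, independently of ED visit or readmission.
- Arm knowledge removes such a test in d = 5 or 10 of 100 device patients.
- Triage has no effect.

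**Step 1. The plan's own figure.** The device rate is 0.48 × (1 − 0.375) = 0.30, and the mean rate is 0.39. With pooled variance under the null:

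z = [0.18 × √120 − 1.96 × √(2 × 0.39 × 0.61)] / √(0.48 × 0.52 + 0.30 × 0.70) = (1.972 − 1.352) / 0.678 = 0.914

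Power is 82.0%, or 82.7% by exact binomial enumeration. The stated power condition is met.

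**Step 2. No overlap.** Suppose every removed test turns an event patient into a non-event patient, on the 48% base. The probability that the uncorrected chi-square is significant in favour of the device (z > 1.96, summed over all pairs of binomial counts) is:

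| Control | Device | Favours device |
|---|---|---|
| 48% | 48% | 2.3% |
| 48% | 43% | 11.3% |
| 48% | 38% | 34.5% |

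This overstates the effect, because some of these patients would also have an ED visit or readmission and would stay events. The base does not fit well either: Section 9.2 builds it as 24% + 2 × 12% = 48%, with the tests occurring at ED or hospital presentation, so it contains no tests planned at discharge.

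**Step 3. Overlap allowed.**
- Control composite = 1 − (1 − 0.24)(1 − q)
- Device composite = 1 − (1 − 0.24)(1 − q + d)
- Gap = 0.76 × d, which is 3.8 points for d = 0.05 and 7.6 points for d = 0.10

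| q | Control | Device, d = 0.05 | Favours device | Device, d = 0.10 | Favours device |
|---|---|---|---|---|---|
| 20% | 39.2% | 35.4% | 9.1% | 31.6% | 23.5% |
| 30% | 46.8% | 43.0% | 8.2% | 39.2% | 21.9% |
| 40% | 54.4% | 50.6% | 8.0% | 46.8% | 20.5% |
| 50% | 62.0% | 58.2% | 9.0% | 54.4% | 22.4% |

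For scale, 7.6 points is about 9 patients of 120 (0.076 × 120 = 9.1). With 58 of 120 control events, the smallest significant result is 43 of 120 in the device arm, a gap of 15 patients or 12.5 points.

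**The case against.** **The window is narrow.** Discharge home must already be planned under the Study Summary criteria, Section 5 randomizes at discharge, and planned staged PCI is excluded. This stands in part. But a planned discharge home fixes neither a date nor a list of tests, and the timing statements disagree.

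**Routine tests may not count.** If related testing is the governing definition, a test planned at discharge may fall outside the endpoint. This stands as a condition on the point. The section that defines the primary outcome omits the limit, and no one is assigned to judge it.

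**Fewer tests may be an intended effect.** In an open-label comparison of care strategies, less testing because a home ECG exists could be seen as part of the benefit. Section 9.2, however, ties the expected effect on testing to the ECG together with phone triage directing care. Orders written before any ECG is sent are not that mechanism.

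**Later ordering stays unblinded.** True. Patients know they have the device, and ECGs enter the medical record. The point concerns only the part that can be prevented.

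**Stronger readings to avoid.** A reader might infer that the cardiologist can also bias the result through discharge drugs. Both arms receive guideline therapy in the same terms, and drugs are not an endpoint component, so the documents do not support that route. A reader might also infer that the start of follow-up is shown to depend on the arm. No section says the cardiologist sets the discharge date or books follow-up tests. Both are reasonable inferences from the treating team's role, not stated facts.

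**Conclusion.** The concern holds in a limited form. The arm is disclosed before the patient leaves, nothing requires the discharge plan to come first, and under Section 9.5.1.1 a test planned or deferred at discharge counts as a primary event. Under the wording of Sections 1, 3.1 and 9.2 it may not, so the exposure turns on an unresolved definition.

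The protocol gives no size for the bias. On the overlap assumptions, changed planning in 5 or 10 of 100 device patients raises the chance of a spurious win for the device from about 2.3% to about 8-9% or 21-24%. A reader might take 11% and 35% as the expected size. On the plan's 48% base they are upper bounds, since they require that no affected patient has another qualifying event. The point deserves a change to the protocol because the remedy is cheap, not because bias has been shown.

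**What to change.** 1. In Section 8.1.2, settle one statement of when randomization occurs and align the Study Summary, Section 5 and the Schedule of Evaluations with it.
2. In the same section, require that the discharge decision and a list of follow-up tests and visits already planned be recorded and time-stamped before the REDCap allocation is opened and disclosed.
3. Reconcile Section 9.5.1.1 with the Study Summary, Section 3.1 and Section 9.2. Tests on the pre-allocation list should be identifiable and should not count as primary events, or should be removed in a prespecified sensitivity analysis. If listed tests do not count, cancelling one after disclosure cannot alter the primary result.

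The cost is protocol wording and one gate in a system that Section 10.2 already uses for randomization. The downside is that allocation and device teaching move closer to departure. Tests added after disclosure, and knowledge of the arm during the 90 days, are not addressed.

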8.1 Schedule of Evaluations

Assessment	Screening, Enrollment, Randomization: pre-discharge (Day 0)	Week 1 (-3,+6 days)	Week 2 (-3,+6 days)	Week 4 (-3, +6 days)	Day 90 (Final) (+/- 7 days)
Informed Consent Form	X (R)				
Demographics	X				
Medical History	X				
Vital signs	X				
Physical Examination	X				
Current Medications	X				
Blood Chemistries	X				
Electrocardiogram	X				
Echocardiogram	X*				
Inclusion/Exclusion Criteria	X (R)				
Enrollment/ Randomization	X (R)				
Providing Device + Instructions	X (R)				
Quality of Life questionnaire (day 0)	X (R)				
Follow-up ECG and training call		X (R.S.)	X (R.S.)	X (R.S.Q)	
End of participation phone call, will include:					X (R)
• ED visits/Hospitalizations/MACE data /ccs					X (R)
• Current medications and if changed lately					X (R)
• Quality of Life questionnaire (day 90)					X (R)
Device collection (patient sending by mail)					X (R)

X Performed as standard of care (not specific for research)

X* If performed after the AMI event and pre-discharge

X (R) Research related only

X (R.S.) Research – Study group related only

X (R.S.Q) Research – Study group related only, depends on the need of further training beyond the first two tests.

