In case of delay with conducting the phone call to the participant, >15 minutes from sending the ECG, or having any technical issues with recording the ECG, the participant will call to a study phone (number provided to the participant) carried by CICU NP/PA which is available 24/7. An alternative phone number will also be provided that will get the patient in touch with the Mayo Clinic operator who can then direct the patient to the Cardiac Intensive Care Unit (CICU) NP/PA staff. Patients will be instructed to use this if they are unable to reach the NP/PA staff directly with the previously provided phone number. In case the technical issue was not solved by the NP/PA, the recommendation for the patient will be based on the symptoms characteristics (as described in the NP/PA decision making tool). In case the participant cannot be reached by the primary phone number provided, NP/PA will call second provided phone number (of patients' related individual/significant other), in case there is no response to both phone numbers, and the participant did not call our NP/PA designated phone, further decisions will be based on the ECG tracing. If alarming findings are present, which may explain a loss of consciousness, EMS will be activated to the home address of the patient, assuming that patients will use the ECG device at home. If no alarming finding is present the patient will be reassured with a phone follow-up the next day.

Adverse Event Reporting

We will only be collecting adverse events that result in Cardiovascular Events, Emergency Department visits, and Hospitalizations, which will be looking at the outcomes, as this is a monitoring study, with no adverse events expected from the device (SmartHeart, which is FDA approved), as all other events are not relevant to the research study. To make sure assessments are consistent throughout the study, this will also be followed retrospectively.

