9. STATISTICAL CONSIDERATIONS

9.1. General Design Issues

This study will be conducted as a parallel group randomized clinical trial. The main goal is to define if Smartheart 12 lead ECG home device will decrease the rates of ED visits and rehospitalization in patients after index hospitalization for acute MI.

Our central primary hypothesis is that the Smartheart 12 lead ECG home device will decrease the ED visits and rehospitalization rates, leading to subsequent decrease in healthcare costs. Additional potential benefit is decrease in mortality by identifying any cardiac emergency at the early stage with appropriate urgent medical assistance. The quality of life of patients with the Smartheart device at home could be improved, knowing there is an easily available tool which can provide quick and reliable diagnosis.

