9.2. Sample Size and Randomization

Patients will be randomized to either standard medical therapy or the medical therapy plus the Smartheart 12 lead ECG home device.

The primary combined endpoint parameter is the rate of ED visits/rehospitalizations as well as related downstream cardiovascular testing (echocardiogram, stress test or coronary CT, or invasive coronary angiogram) at 90 (+/-7) days after discharge and mortality rates during the 90 (+/-7) days of follow up. Based on the most recent in-house registry data, we have about 50 AMI patients undergoing PCI a month. Accordingly, we have at least 600 patients a year who are discharged with a diagnosis of AMI from Saint Mary's Hospital.

Our own registry data further indicate that 24% of revascularized AMI patients will present to the ED or will be readmitted within 90 days. This is in keeping with the published literature citing a rate of 20-30%. Half of these patients will present for cardiovascular complaints and may get further testing, including echocardiogram, stress test or coronary CT, or invasive coronary angiogram. Having a 12-lead ECG available and the phone triage available to direct care may impact not only emergency presentation but also downstream testing. This will be considered in this trial, and each of these will be considered as a component to the combined primary endpoint event. Assuming that patients presenting with cardiovascular concern may receive two of the outlined downstream test as they present to the ED and hospital, the estimated event rate will be 48%. With 120 patients in each arm the study we would be adequately powered (beta error <0.2) to show a statistically significant (at alpha error levels of <0.05) for a 37.5% event reduction.

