In the event that a subject revokes authorization to collect or use PHI, the investigator, by regulation, retains the ability to use all information collected prior to the revocation of subject authorization. For subjects that have revoked authorization to collect or use PHI, attempts should be made to obtain permission to collect at least vital status (long term survival status that the subject is alive) at the end of their scheduled study period.

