APPENDIX A

DATA AND SAFETY MONITORING PLAN

Table 1. Enrollment by Month of Study

Month	# Expected	# Screened	# Enrolled or Randomized	# Withdrawn	# Actual (# Enrolled - # Withdrawn)	# Cumulative (Sum of # Actual by Month)
1						
2						
3						

Table 2. Demographics

Characteristics	N	N%
Gender		
Female		
Male		
Age		
Mean (SE)		
Median (min, max)		
<34 years		
34-44 years		
45-54 years		
55-64 years		
65-74 years		
75-84 years		
>84 years		
Ethnicity		
Hispanic or Latino		
Not Hispanic or Latino		
Unknown		
Race		
AIAN		
Asian		
Nat Hawaiian/Other Pac Islander		
Black or African American		
White		
Other		
More than one race		
Unknown		

Table 3. Subject Status

Pt Identifier	Date Enrolled	Date Completed Study	Study Status	Reason for Withdrawal	% Adherence to Intervention	Intervention Duration (Weeks)
Subj001						
Subj002						
Subj003						

Status:

A = Active

C = Completed

W = Withdrawn

L = Lost to follow-up

% Compliance to Intervention: $(\# \text{ tablets taken}/\text{total } \# \text{ per protocol}) * 100$

or

 $(\# \text{ classes taken}/\text{total } \# \text{ of sessions should have attended}$

per protocol) * 100

Table 5. Frequency of Specific Symptoms

Symptoms	AE Code (MedRA, CTCAE)	N%
Fatigue		
Dyspnea		
Palpitations		
(Pre-)Syncope		
Chest pain		

Table 7. Subject Deaths

Pt Identifier	DOB	Date Enrolled	Treatment Date	Cause of Death	Date of Death	Comments
Subj001						
Subj002						
Subj003						

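### Mortality is part of the primary endpoint in 9.2 but not in 9.5.1.1, and the collection rules do not capture all deaths

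*Combined protocol and SAP*

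**What the plan says.** **Whether death is an outcome.** Section 9.2 describes the primary combined endpoint parameter as ED visits or rehospitalizations with related testing, "and mortality rates during the 90 (+/-7) days of follow up". It does not say whether this means death from any cause. Section 9.5.1.1 gives a different definition: "The combined primary endpoint of the trial is the rate of ED visits, hospital readmission, and any of the downstream testing modalities", and death is not listed. Section 9.1 names mortality as a hoped-for gain: "Additional potential benefit is decrease in mortality by identifying any cardiac emergency at the early stage". The MACE definition in the Study Summary (Objectives) includes cardiovascular death but no other death.

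**What is collected.** The adverse event paragraph in Section 5 says "We will only be collecting adverse events that result in Cardiovascular Events, Emergency Department visits, and Hospitalizations", treats other events as not relevant to the study, and adds that these outcomes will also be followed retrospectively. In the Schedule of Evaluations (8.1), the outcome item is "ED visits/Hospitalizations/MACE data /ccs", gathered in the end-of-participation phone call. The event list in 10.2 names cardiac dysfunction or heart failure, MI, arrhythmia, TIA and stroke.

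**Where death or vital status does appear.** Section 11 says that "attempts should be made to obtain permission to collect at least vital status", but only for patients who revoke authorization to use their health information. Appendix A has a table of deaths with cause and date. The status codes in its Table 3 are active, completed, withdrawn and "L = Lost to follow-up".

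**The concern.** The intervention includes telling patients with a reassuring ECG that they can defer seeking care (4.2). Death at home is the harm most relevant to that advice, and it produces no ED visit, no readmission and no test. Section 4.1 adds that, among post-MI patients followed for about four years, roughly a quarter of the sudden deaths fall in the first three months, which is this trial's window.

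Three things are at stake:

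- The mortality comparison implied by 9.2 may be incomplete.
- Under 9.5.1.1, a patient who dies at home before any visit or test has no primary event, so the worst outcome is scored as a good one.
- Whether a death counts in MACE depends on its being called cardiovascular. Allocation is known to the patient and the treating cardiologist (8.1.2), and there is no adjudication committee (Section 13).

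**Working it through.** **1. The routes by which a death could reach the data**

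| Route | What it reaches | What it leaves out |
|---|---|---|
| MACE, listed for the day-90 call (Study Summary, 8.1) | Cardiovascular death | Other or unknown cause; no rule if nobody answers |
| Adverse event rule (Section 5) | Cardiovascular events, ED visits, hospitalizations | Death at home not attributed to a cardiovascular cause |
| Retrospective follow-up (Section 5) | The same events | No source or method given; death not named |
| Event list (10.2) | Five non-fatal categories, possibly not exhaustive | No death item |
| Second phone number (Section 5) | Patients who have transmitted an ECG and cannot be reached | Controls; the day-90 call |
| Vital status (Section 11) | Patients who revoke authorization | Everyone else |
| Deaths table (Appendix A) | A place to list deaths | No procedure that supplies them |

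Suppose a patient dies at home of unknown cause without an ED visit. No row obliges anyone to find that death. The day-90 call goes unanswered, and the patient is carried as lost, or as event-free if the record shows no visit or test.

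**2. Scheduled contacts by arm**

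The Schedule marks the Week 1, 2 and 4 calls as study group only, with Week 4 as needed. After discharge the device arm therefore has three or four scheduled contacts (Weeks 1 and 2, possibly 4, and day 90); controls have one. The extra calls can reveal only deaths in about the first month. After that, the device arm's additional signals are an ECG transmission or a device that is not mailed back.

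**3. Effect on primary power**

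Inputs from 9.2: control rate 0.48; relative reduction 37.5%, so 0.48 × (1 − 0.375) = 0.30; n = 120 per arm; alpha 0.05, taken as two-sided because the plan does not say.

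Power = Φ{[|p1 − p2|√n − 1.96√(2p̄(1 − p̄))] / √[p1(1 − p1) + p2(1 − p2)]}, with p̄ = 0.39.

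(0.18 × 10.954 − 1.96 × 0.690) / 0.678 = 0.914, and Φ(0.914) = 0.820. The plan's claim of at least 80% power reproduces.

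The documents give no 90-day post-discharge mortality, so I assume 1% to 5%, equal in both arms, with every death unseen. If deaths become losses, n falls to 120(1 − m), rounded. If they are scored event-free, each rate becomes p(1 − m). The last column shows the alternative of counting deaths as extra primary events, p + m(1 − p).

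| Assumed m | Deaths per arm (120m) | Power, lost (n) | Power, event-free | Power, counted as events |
|---|---|---|---|---|
| 1% | 1.2 | 0.817 (119) | 0.813 | 0.810 |
| 2% | 2.4 | 0.813 (118) | 0.807 | 0.800 |
| 3% | 3.6 | 0.807 (116) | 0.800 | 0.789 |
| 5% | 6.0 | 0.800 (114) | 0.787 | 0.769 |

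**4. Effect on the mortality comparison**

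One missed death, as a share of an arm's expected count, is 1/6.0 = 17% at 5% mortality and 1/1.2 = 83% at 1%. The question is likely to arise: at 1% mortality, the chance of at least one death among 240 patients is 1 − 0.99^240 = 0.91.

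**5. Near the significance boundary**

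With 58 of 120 control events (48% of 120 is 57.6), 43 events in the device arm give p = 0.0499 and 44 give p = 0.068 (chi-square, uncorrected). A single patient coded differently matters there, but only there: at the design values, 58 against 36, p = 0.004.

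**The case against.** The strongest reply is that the gap is narrower than it looks. Much of it stands:

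- **All-cause death as a promised outcome.** A reader might infer this from 9.2. The text says only mortality rates, once, in the sample-size section. The objectives in Section 3 and the outcome measures in 9.5 do not list mortality, apart from cardiovascular death within MACE. What the documents show is a conflict between 9.2 and 9.5.1.1.
- **No death being captured at all.** This is not supported either. Cardiovascular death is in MACE, and MACE is collected in both arms at day 90. Early sudden death after MI would ordinarily be counted there, once it is known.
- **The phone call as the only route.** It is the only scheduled outcome contact shared by both arms, but Section 5 adds retrospective follow-up. Section 11 refers to linkage with medical records, 10.1 requires missing data to be explained, and a caring family member is an inclusion criterion. None of these names death or says what to do when the call fails, so they soften the point without closing it.
- **The missing status code as a rule that turns deaths into losses.** Table 3 is an unadapted template: it defines compliance by tablets taken and classes attended. The missing code is weak evidence of intent, and Appendix A does contain a deaths listing.
- **Few deaths, small effect.** With 1 to 6 expected deaths per arm, the direction of a mortality comparison is unstable even with perfect ascertainment, and this is a self-described pilot. That is true, but it is no reason to add avoidable and possibly unequal error to so small a count.

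**Conclusion.** The point holds in a limited form. Sections 9.2 and 9.5.1.1 disagree on whether death belongs to the primary endpoint. The stated rules also leave an out-of-hospital death of non-cardiovascular or unknown cause without a reliable route into the data. Followed literally, the plan can record such a death as lost or event-free. Detection may differ by arm because controls have fewer scheduled contacts.

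A reader might infer that the primary result is compromised. The figures do not support that. Even if every death were missed, at an assumed 1% to 5% mortality equal in both arms, power would move from 0.820 to between 0.787 and 0.817. The exception is a result close to the boundary combined with unequal miscoding.

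The damage is to the mortality, MACE and safety comparisons, where one death can be 17% to 83% of an arm's expected count. That range rests on the assumed mortality. The documents do not show that deaths will in fact be missed, only that no stated procedure prevents it. The change should be made, mainly because it is cheap.

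**What to change.** 1. Reconcile 9.2 and 9.5.1.1 on whether death is part of the primary endpoint. In 9.6, state how a patient who dies enters the chi-square analysis, including one who dies before any visit or test.
2. Add vital status at day 90, with date and cause of death, to the Schedule of Evaluations (8.1) and to the adverse event rule in Section 5, for every randomized patient in both arms.
3. Name the sources: the medical record and, if the call is unanswered, a family contact number collected at enrollment in both arms.
4. Record death as its own status, separate from lost to follow-up.
5. Report all-cause death by arm alongside cardiovascular death. All-cause death does not depend on an unblinded, unadjudicated judgement of cause; cardiovascular death does.

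The cost is one CRF item, one status code, one phone number per patient and a few extra calls to non-responders. If death is made a primary event, the last column of the power table shows the price at the present sample size: 0.810 to 0.769 at 1% to 5% mortality, if mortality is equal in both arms.
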